4.4.2 Maternal Secondary Outcomes

- Patient satisfaction as measured by patient satisfaction/pain/anxiety surveys.
- Vaginal delivery rate
- Operative Vaginal delivery rate.
- Cesarean delivery rate.
- Start of oxytocin until delivery
- Time of delivery until discharge
- Time of admission until discharge

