2.2 Purpose and Rationale for Study

This trial is looking at patient satisfaction and cost comparison between inpatient and outpatient preinduction cervical ripening. The method will be compared with inpatient pre-induction cervical ripening and patients admitted to the hospital in labor. Time from initiation of method, time in labor and delivery and time from onset of labor to delivery, and rate of achieving a vaginal delivery within 24 hours will be evaluated.

This protocol outlines a randomized trial of 200 women evaluating placement of Cervidil to the posterior vaginal fornix to soften the cervix in preparation for induction of labor. 100 patients will be randomized into the inpatient cervical ripening arm, and 100 to the outpatient cervical ripening arm. The study will not be powered for fetal or newborn mortality.

Increasing patient comfort, patient satisfaction, and inpatient costs will benefit future patients and healthcare for women who require/desire induction of labor.

2.3 Product being investigated:

Cervidil (outpatient cervical ripening) – Cervidil

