3.7.3 Concomitant Medications

- 1. Excluded medications include other uterotonics (example: oxytocin) while Cervidil remains in place.
- 2. Known hypersensitivity to prostaglandins.

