- 6) The patient remains for further evaluation if any of the following are noted. (If the patient must remain for any of these reasons, she will need an evaluation by her attending MD or the Hospitalist prior to discharge.):
 - a. Category 2 or 3 tracing
 - b. Vaginal bleeding (beyond spotting from placement of Cervidil insert)
 - c. Any abnormal maternal vital signs (as defined in Intermountain Healthcare Standard Practice Guidelines)
 - d. ROM
 - e. More than 1 contraction every 10 minutes is noted in the last 30 minutes of monitoring.
 - f. If the insert is inadvertently dispelled from the vagina, a new insert should be placed within 15 minutes and the participant may still be discharged if she meets criteria. (The vaginal insert releases prostaglandin at a rate of 0.3 mg/hr so replacing the insert within 15 minutes will not change the overall effect of the medication)
- 7) Patient will remove the insert and return to the hospital:
 - a. For spontaneous rupture of membranes
 - b. For vaginal bleeding
 - c. Consistent contractions closer than every 10 minutes
 - d. Severe pain
 - e. Decreased fetal movement
 - f. Temperature over 100.5 degrees F.
- 8) When admitted to L&D for induction as outpatient in a bed:
 - a. Admission history and physical is done by labor nurse
 - b. Cervidil is removed and Bishop score is documented.
 - c. Results of exam are given to the attending provider.
 - d. If appropriate, Pitocin induction of labor is started per Intermountain Healthcare Standard Practice Guidelines.
- 9) Cervidil placement should not exceed 12 hours.
 - a. Management of induction per Intermountain Healthcare Standard Practice Guidelines continued at the discretion of the admitting provider.
 - b.

4.2.2 For participants randomized to the inpatient cervical ripening arm:

The patient is scheduled in L&D for:

1) Admission as "outpatient in a bed" in iCentra for hospital placement of Cervidil.

- a. The patient's priority is based on the maternal and fetal condition compared to other scheduled inductions.
- 2) Induction of labor.

Preadmission:

The patient will have education and consent to the procedure prior to admission.

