- The patient will be admitted to L&D ("outpatient in a bed" status in iCentra) and placed on the fetal monitor. The clinician or hospitalist will perform an ultrasound for assessment of amniotic fluid volume by deepest vertical pocket (DVP) and review the fetal heart tracing. If the fetal heart rate is reactive (Category I) and the DVP is > 2cm the procedure may proceed once ordered by the attending obstetric provider or OB hospitalist.
- 2) Nursing or research staff member completes the outpatient cervical ripening CRF.
- 3) If the fetal heart rate is reactive (Cat I) and the DVP is >2cm the procedure may proceed once ordered by attending obstetric provider or OB Hospitalist.
- 4) The cervix is examined: Requirements of exam to do cervical ripening
 - a. Cervix is dilated less than 3cm
 - b. Presenting part is vertex
 - c. The provider places the Cervidil into the posterior vaginal fornix with the string at the introitus.
 - d. The provider is available for immediate phone consultation by the patient or nursing staff and is readily available to L&D.
- 5) The patient is watched with continuous fetal monitoring for 2 hours.
- 6) The patient remains hospitalized
 - a. If the insert is inadvertently dispelled from the vagina, a new insert should be placed within 15 minutes and the participant may still be discharged if she meets criteria.
 (The vaginal insert releases prostaglandin at a rate of 0.3 mg/hr so replacing the insert within 15 minutes will not change the overall effect of the medication)
- 7) The Cervidil may be removed and induction of labor per Intermountain Healthcare Standard Practice Guidelines may be started per discretion of the admitting provider for any of the following:
 - a. For spontaneous rupture of membranes
 - b. For vaginal bleeding
 - c. Consistent contractions closer than every 10 minutes
 - d. Severe pain
 - e. Decreased fetal movement
 - f. Temperature over 100.5 degrees F.
 - g. Document dat/time of Cervidil removal
 - h. Document Bishop score
- 8) Cervidil placement should not exceed 12 hours.
 - a. Management of induction per Intermountain Healthcare Standard Practice Guidelines continued at the discretion of the admitting provider.

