5.3 Analysis Plan

Primary analysis will be done using 2 sample t-tests on the numeric outcomes with the possibility of using the log of the outcome when the outcome is skewed (as is common for waiting times and cost variables). If the data is not sufficiently normal after logging, then a 2 sample permutation test on the means will be used instead. For categorical outcomes (e.g. delivery type) a chi-squared test will be used to compare the proportion in each category between the treatment and control groups. All tests will be performed at a 5% significance level. The p-values will be reported both unadjusted for multiple outcomes and also adjusted using the False Discovery Rate method. Conclusions will be made using the unadjusted values since each outcome is of interest by itself and they are predetermined.

Additional exploratory data analysis will be done using linear model including regression and logistic regression to adjust for other variables of interest. Any interesting results will be reported as exploratory with need for confirmation since the potential results are not on a predetermined list.

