6.3 Performance Monitoring

The following data elements will be collected.

- Participant ID
- Age
- EDC
- Method of Dating
- G/TPAL
- Date/Time
 - Hospital evaluation
 - Bishop score prior to placement of cervidil insert
 - Bishop score on admission upon removal of Cervidil insert
 - Time of insertion
 - Time Home
 - Time of readmit
 - Reason for readmit (see above reasons to return to L&D)
 - Time of removal of Cervidil insert
 - Time Pitocin started
 - Epidural- if placed and if so when
 - Delivery time
 - Method of delivery
 - Spontaneous vaginal
 - Operative vaginal
 - C-Section
 - Indication if other than spontaneous vaginal delivery
- Apgar, weight, cord pH if done

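### Oxytocin-to-delivery time exists only for women who are given oxytocin, so its t-test compares subsets selected after randomization and can dilute a real difference or create a small false one

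*Combined protocol and SAP*

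**What the plan says.** Section 4.4.2 lists "Start of oxytocin until delivery" with no analysis population and no rule for a woman who never receives oxytocin.

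Oxytocin is conditional in both arms:
- Outpatient arm (4.2.1, step 8d): "If appropriate, Pitocin induction of labor is started per Intermountain Healthcare Standard Practice Guidelines".
- Inpatient arm (4.2.2, step 7): after removal of the insert, induction "may be started per discretion of the admitting provider for any of the following", followed by a list of triggers.

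Both arms list "Consistent contractions closer than every 10 minutes" among the triggers, so labor brought on by the insert alone is foreseen. Section 3.7.3 states "Excluded medications include other uterotonics (example: oxytocin) while Cervidil remains in place", so a start time can arise only once ripening has ended.

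On analysis, section 5.3 says "Primary analysis will be done using 2 sample t-tests on the numeric outcomes". It gives no rule for undefined values. It reports p-values both unadjusted and adjusted for false discovery rate, and draws its conclusions from the unadjusted ones, outcome by outcome.

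Section 2.2 promises to evaluate "Time from initiation of method, time in labor and delivery and time from onset of labor to delivery", but the first of these intervals is absent from the outcome lists in 4.4. The data list in 6.3 has "Time Pitocin started", along with insertion and delivery times, but no item for oxytocin not given.

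**The concern.** A woman who labors on the insert and delivers without oxytocin has no value for this outcome. Section 5.2 does not remove her from the trial, since it withdraws only women who labor before the planned ripening date. She simply drops out of this one comparison, and she is likely to be among those who responded best to ripening. The women left are chosen by a post-randomization event that may depend on the arm, so randomization no longer protects the contrast.

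The arms share the same insert and the same list of triggers, but not the same setting. An inpatient provider can act on site; a woman at home removes the insert, travels in and is assessed on return. The share going without oxytocin could therefore differ between arms. Because 5.3 lets each outcome carry its own conclusion at an unadjusted 5% level, a distorted result here would be reported as a finding about outpatient ripening.

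**Working it through.** **The plan's own figure.** Section 5.1.1 claims 95% power at 0.36 SD and 80% at 0.28 SD with 200 per group. A two-sided 5% test gives 94.95% and 79.96%, so both reproduce. No figure is stated for the oxytocin interval.

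**Detectable difference here.** Section 2.2 plans 100 per arm. If 15% and 30% have no value, 85 and 70 women remain. The 80%-power difference is (1.960 + 0.842) × √(1/85 + 1/70) = 2.802 × 0.1614 = 0.45 SD. This, not 0.28 SD, is the yardstick for the results below.

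**Model (assumed).** Readiness R is standard normal. Women with R above a cutoff c labor without oxytocin; their share is q, so c = z(1−q). The mean of R among the rest is −φ(c)/Φ(c):
- q = 0.15: c = 1.036, mean −0.274
- q = 0.30: c = 0.524, mean −0.497

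Time is shorter with higher R, with correlation ρ. The values of q and ρ are assumptions; the documents give neither.

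**Case A: ripening is better in one arm, same cutoff in both.** Shares of 15% and 30% imply a true shift of 1.036 − 0.524 = 0.51 SD in readiness. Among the women left, the means are −0.274 and 0.512 − 0.497 = 0.015, a difference of 0.29 SD. The direction is right and the size is cut by over 40%. These figures are for ρ = 1; a smaller ρ scales both equally (at 0.5, 0.26 appears as 0.14). At 10% versus 20%, 0.44 appears as 0.28. On the 2-hour SD of the 5.1.1 example (which is for admission to delivery, so only indicative), with ρ = 0.5, a shift of 0.5 SD and shares of 20% and 37%, a true benefit of 30.1 minutes appears as 15.6.

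**Case B: identical ripening, different readiness to start oxytocin.** The true difference is zero. The women left differ by 0.497 − 0.274 = 0.22 SD at ρ = 1 and 0.11 SD at ρ = 0.5; the arm with fewer oxytocin starts looks slower. At 10% versus 20% the values are 0.155 and 0.077 SD.

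Rejection rate of the nominal 5% test at 15% versus 30%, ρ = 0.5: 0.111/0.1614 = 0.69 standard errors, so P(Z > 1.27) + P(Z < −2.65) = 0.102 + 0.004, or about 10%. Simulation with 100 per arm at a wider contrast, 10% versus 30%, gives 8.1%, 16.9% and 30.4% for ρ = 0.3, 0.5 and 0.7.

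**Null cases.** With equal q in both arms, or ρ = 0, the bias is zero.

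**The case against.** Both arms receive the same insert under the same 12-hour limit, have the same removal triggers, and refer induction to the same institutional guidelines. A difference in the oxytocin-free share is therefore possible but not shown, and a two-fold difference is only an illustration. The inpatient arm also has a Bishop score documented with removal, so the assessment contrast is weaker than it first looks. Women who contract on the insert and later receive oxytocin have a start time and stay in the analysis. This is one of seven maternal secondary outcomes; the primary time outcome and admission-to-discharge time do not depend on oxytocin use. All of this stands, and it limits the importance of the point.

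A reader might go further and infer that the arm with better ripening will look slower, so that the sign is wrong. The documents do not support that. For a normal variable cut at a common threshold, the mean of what remains rises with the underlying mean, so better ripening gives dilution and not reversal (Case A). A spurious or reversed difference needs different thresholds for starting oxytocin, or an effect that varies between women. The discretion in 4.2 permits this but does not establish it. Nor should 0.11 to 0.22 SD be set against the 0.28 SD target, which assumes 200 per group.

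The objection does not remove the core: the value is undefined without oxytocin, the plan has no rule for that, and 5.3 attaches a stand-alone conclusion to the test.

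**Conclusion.** The point holds in a limited form. Followed as written, the plan tests this interval in women selected after randomization by their response to ripening and by provider discretion, so the result is not a comparison of the randomized arms. The more natural consequence, if ripening differs, is dilution: 0.51 SD seen as 0.29 SD at 15% versus 30%. If only the readiness to start oxytocin differs, the test can show a false difference of about 0.11 SD at correlation 0.5, with a rejection rate of about 10% in place of 5%. Both sizes rest on assumed shares, an assumed correlation and a normal model. The claim that the outcome will favor the arm where ripening worked less well is not established.

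**What to change.** In 4.4.2, test two outcomes in all randomized women who received the insert:
1. Time from Cervidil insertion to delivery, which 2.2 already intends.
2. The proportion receiving oxytocin, by the chi-squared test already in 5.3.

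In 6.3, add an explicit entry for oxytocin not given, so that a blank start time is not ambiguous. Report oxytocin-to-delivery time by arm as a description among recipients, with their number, and draw no between-arm conclusion from it.

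The cost is outcome-list wording and one data field; insertion, Pitocin start and delivery times are already collected, and care does not change. The downside is that the tested interval is longer and more variable. The new population also leaves out women withdrawn between randomization and insertion (5.2). That selection is not driven by response to the insert, but the withdrawals should be reported by arm.

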1.2 Study Hypotheses

When compared to patients admitted to the hospital for cervical ripening:

- From the time of admission ("outpatient in a bed" status by iCentra, our EMR), patients in the outpatient cervical ripening arm will progress to complete cervical dilation in less time.
- The total overall cost of care for the encounter will be reduced for the group in the outpatient cervical ripening arm.
- Patients in the outpatient cervical ripening arm will have more overall satisfaction.

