3.1 Primary Objectives

To show that when compared to patients admitted to the hospital for cervical ripening:

- a. From the time of admission, patients in the outpatient cervical ripening arm will progress to the second stage of labor in less time.
- b. Patients in the outpatient cervical ripening arm will have more overall satisfaction.
- c. The total overall cost of care for the encounter will be reduced for the group in the outpatient cervical ripening arm.
- d. Patients in the outpatient cervical ripening arm will spend less total time in the hospital.
- e. Cesarean section rates will be similar.

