4.2 Study Procedures

Eligible and consenting patients will be randomized by a certified research staff member using an internet based randomization system maintained by the Women and Newborn Research department. The patient will be assigned to either the inpatient or outpatient cervical ripening group. Patients will be consented and randomized at the time the patient is being scheduled for their induction. If for any reason a research staff member is unavailable to consent the patient at the time the induction is being scheduled, a time will be set for the Cervidil placement as well as a time for the induction and consent/randomization will be scheduled prior to Cervidil placement. If they are randomized to the "inpatient group" then the following induction appointment will be cancelled.

When the participant comes in for their scheduled induction, eligibility criteria will be verified again.

4.2.1 For participants randomized to the Outpatient cervical ripening arm:

- The patient will be an outpatient in L&D ("place in observation" status in iCentra) and placed on the fetal monitor. The clinician or hospitalist will perform an ultrasound for assessment of amniotic fluid volume by deepest vertical pocket (DVP) and review the fetal heart tracing. If the fetal heart rate is reactive (Category I) and the DVP is > 2cm the procedure may proceed once ordered by the attending obstetric provider or OB hospitalist.
- 2) Nursing or research staff member completes the outpatient cervical ripening case report form (CRF).
- 3) The cervix is examined and Bishop score is documented: Requirements of exam to do cervical ripening
 - a. Cervix is dilated less than 3cm
 - b. Presenting part is vertex
 - c. The provider places the Cervidil into the posterior vaginal fornix with the string at the introitus.

- d. The provider is available for immediate phone consultation by the patient or nursing staff and is readily available to L&D.
- 4) The patient is watched with continuous fetal monitoring for 2 hours.
- 5) The patient is discharged to home if all of the following are present:
 - a. Category 1 tracing X2 hours.
 - b. No vaginal bleeding
 - c. Normal maternal vital signs.
 - d. Intact BOW
 - e. Less than 1 contraction every 10 minutes at the time of discharge.

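### Admission-to-discharge time leaves out the outpatient arm's placement visit, so the saving in total hospital time (objective 3.1d) is overstated by at least 2 hours per woman sent home

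*Combined protocol and SAP*

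**What the plan says.** - **Objective.** Section 3.1, item d: "Patients in the outpatient cervical ripening arm will spend less total time in the hospital".
- **Measure.** Section 4.4.2 lists "Time of admission until discharge". No other outcome in section 4.4 measures total time in the hospital. Section 3.3.1 names date and time of discharge as a primary endpoint but gives no starting point.
- **Meaning of admission.** The first hypothesis in section 1.2 begins: "From the time of admission ('outpatient in a bed' status by iCentra, our EMR".
- **Outpatient arm, placement visit (4.2.1, step 1).** "The patient will be an outpatient in L&D ('place in observation' status in iCentra) and placed on the fetal monitor". Ultrasound, examination and insertion follow. Step 4 then says: "The patient is watched with continuous fetal monitoring for 2 hours". Only after that may she go home.
- **Outpatient arm, return (4.2.1, step 8).** The admission status appears here: "When admitted to L&D for induction as outpatient in a bed".
- **Inpatient arm (4.2.2).** "The patient will be admitted to L&D ('outpatient in a bed' status in iCentra) and placed on the fetal monitor". This comes before the ultrasound, examination, insertion and the same 2 hours of monitoring.
- **Dwell time (both arms).** "Cervidil placement should not exceed 12 hours".
- **Data collected (6.3).** The list includes *Hospital evaluation*, *Time of insertion*, *Time Home* and *Time of readmit*. It does not include discharge time.

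**The concern.** The objective is about hours in the hospital, but the measure counts hours since a particular electronic status. The two agree for a woman who stays from placement to discharge. They do not agree for a woman who is worked up and monitored in L&D, goes home, and is given the admission status only when she returns. Her placement visit occupies L&D and drops out of the measure, while the same steps count in full for a woman in the comparison arm. The omission always favours the hypothesis.

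What is at stake is the size of the claimed saving. Hospital time is one of five primary objectives, and section 5.3 draws conclusions outcome by outcome from unadjusted tests at the 5% level. An inflated difference would therefore support a stand-alone statement about hospital time.

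The concern is limited to objective 3.1d. Inpatient ripening hours are real hospital time and belong in the count. The fault is that the outpatient arm's own L&D hours are left out.

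**Working it through.** **1. Where each clock starts.** Let *e* be the time from arrival to insertion (not given), *D* the time from insertion to removal (in the outpatient arm, to return), and *L* the time from then to discharge. Take *L* as equal in both arms; this is an assumption.

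| | True hospital time | Counted by admission-to-discharge |
|---|---|---|
| Inpatient arm | e + D + L | e + D + L |
| Outpatient arm, sent home after 2 h | e + 2 + L | L |

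Measured gap = e + D. True gap = (e + D + L) − (e + 2 + L) = D − 2. Overstatement = (e + D) − (D − 2) = e + 2, so at least 2 h whatever *D* is.

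**2. Share of the measured gap that is artefact, setting e = 0.** Share = 2/D.

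| D | Measured gap | True gap | Artefact |
|---|---|---|---|
| 12 h (documented maximum) | 12 h | 10 h | 2/12 = 17% |
| 8 h (assumed) | 8 h | 6 h | 2/8 = 25% |
| 4 h (assumed) | 4 h | 2 h | 2/4 = 50% |

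Any *e* above zero raises the share, because (e + 2)/(e + D) is larger than 2/D when D exceeds 2. Dwell below the maximum is foreseeable, since 4.2.1 step 7 lists reasons to remove the insert and return. If only a fraction *p* of the outpatient arm goes home, these women shift the arm mean by at least 2*p* h.

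**3. The other reading of admission.** Suppose the clock started at the placement visit instead. The outpatient arm would be counted as e + D + L against a true e + 2 + L. That adds D − 2 hours at home (10 h at D = 12), and the measured gap would be zero. A single interval from admission to discharge cannot equal hospital time for a woman who goes home in between.

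**4. Effect on a test (illustration only).** The plan's own power figures come first, using power = Φ(d/√(2/n) − 1.96), two-sided 5%. Section 5.3 does not state sidedness. With n = 200 per group, √(2/n) = 0.1:
- d = 0.36: Φ(3.6 − 1.96) = 95%, and 0.36 × 120 min = 43.2 min.
- d = 0.28: Φ(2.8 − 1.96) = 80%, and 0.28 × 120 min = 33.6 min.

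Both agree with section 5.1.1. Section 2.2 randomizes 100 per arm, so the illustration uses n = 100. It supposes that true total time is equal and that every outpatient-arm woman is shifted by 2 h. The standard error is SD × √(2/100). The documents give no SD for length of stay, so these SDs are assumptions:
- SD 8 h: 2/1.131 = 1.77, giving 42% of trials with p < 0.05.
- SD 12 h: 2/1.697 = 1.18, giving 22%.
- SD 24 h: 2/3.394 = 0.59, giving 9% (both tails).

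The nominal rate is 5%.

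**The case against.** **Hours at home are a genuine reduction in hospital time.** This stands. A reader might infer that a shorter stay is built in and the whole saving is an artefact. The documents do not support that: at 12 h dwell and with the same later course, about 10 of the 12 measured hours are real. What is built in is a bias of at least 2 h, not the sign of the result.

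**The false-positive rates test an unlikely null.** This also stands. Equal total time would require outpatient-arm women to lose all their hours at home through a longer stay after return, and nothing in the documents suggests that. A reader might also apply the 2 h SD in section 5.1.1, which would make a false positive almost certain. That SD is an example for time from admitting to delivery. Admission-to-discharge also contains the stay after delivery, so the figure cannot be carried over.

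**The omission is inferred.** Section 4.4.2 does not define admission. The status gloss belongs to the time-to-dilation hypothesis, and section 6.3 speaks of a readmission. Section 2.2 also mentions time in labor and delivery. This is fair as far as it goes. However, the section 2.2 wording is not carried into the outcomes of section 4.4, nothing adds the placement visit back, and the other reading fails too (step 3 of the working).

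**It is listed as a secondary outcome.** That is so in 4.4.2, but 3.1 makes hospital time a primary objective and 3.3.1 makes discharge time a primary endpoint.

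**Unadmitted extra visits.** A reader might suppose that some outpatient-arm women return, go home again and are missed. Section 4.2.1 goes from return to admission for induction and describes no second discharge home, so this is not part of the finding.

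**Conclusion.** The point holds as a mismatch between a primary objective and its measure. Followed as written, with admission read as in section 1.2, the plan overstates the saving in hospital time by at least 2 h per outpatient-arm woman sent home, plus pre-insertion time of unknown length. If the later course is the same in both arms, that is about 17% of the measured difference at the documented 12 h maximum, 25% at an assumed 8 h and 50% at an assumed 4 h.

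The 2 h minimum rests on the monitoring period and the status rules in section 4.2 and needs no SD. The percentages rest on equal later course and on the dwell time. The rates of 42%, 22% and 9% are illustrations under assumed SDs and a null that is not expected to hold. The documents do not show that the conclusion on 3.1d would point the wrong way. They also do not say when the clock starts for outpatient-arm women who fail the discharge criteria and stay, so that rule has to be written in any case.

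**What to change.** In sections 4.4.2 and 3.3.1, define total hospital time for objective 3.1d as the sum of the intervals spent in the hospital:

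- Outpatient arm, sent home: (*Time Home* − *Hospital evaluation*) + (discharge − *Time of readmit*).
- Inpatient arm, and outpatient-arm women never sent home: discharge − *Hospital evaluation*.
- Any further L&D visit: add its duration from the EMR if one occurs.

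Base the conclusion on 3.1d on this sum and keep admission-to-discharge as a descriptive result. Record *Hospital evaluation* in both arms.

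The cost is small. Three of the four times are already in the section 6.3 list. Discharge time must be added there or taken from the EMR, as must any further visit. Visits, treatment and sample size do not change. The downside for the sponsor is that the apparent saving becomes smaller.
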